40.	Appendix I	
The row under Tests and Observations reading “SGOT, alkaline phosphatase, bilirubin” was edited to read “SGOT, SGPT, alkaline phosphatase, bilirubin.”
 
The column Following Completion of Protocol Therapy was renamed as Chemo-Radiation Therapy Completion or Premature Treatment Discontinuation.
 
The column After Diagnosis of Recurrence was renamed as 3, 6, 9, and 12 Month Follow-up.
 
The column Premature Treatment Discontinuation was changed to After Diagnosis of Recurrence.
 
In the column Chemo-Radiation Therapy Completion or Premature Treatment Discontinuation, the following indications were removed CT Scan with contrast of pelvis and abdomen; CD4+ T-cell count; and HIV Viral load.
 
In the column 3, 6, 9, and 12 Month Follow-up, the following indications were removed: chest X-ray and serum for HPV-serology.
 
In the column 3, 6, 9 and 12 Month Follow-up, the following indications were added: Physical exam and ART adherence.
 
In the column After Diagnosis of Recurrence, the following indications were removed: Physical exam; ART adherence; and Anal and cervical swabs for HPV-associated disease research.
 
In the column After Diagnosis of Recurrence, the following indications were added: Chest X-ray; CD4+ T-cell Count; and HIV viral load
 
In the column Premature Study Discontinuation, the following indications were added: anal and cervical swabs for HPV-associated disease research; and serum for HPV-serology
 
Footnote 6 “CT with contrast of abdomen and pelvis. Scans are only required if more than 3 months have elapsed since the last CT scan” was removed.
 
Footnote 9 “Anal and cervical swabs and serum for HPV-associated disease research will be collected within 4 weeks following the discontinuation of treatment” has been changed to “Anal and cervical swabs and serum for HPV-associated disease research will be collected on the final day of chemo-radiation therapy or within 4 weeks following the final chemo-radiation therapy.”
 
Footnote 10 “Assessment must be completed within 7 days of the completion of chemo-radiation therapy. This visit is required for all participants and refers both to scheduled completion of treatment and premature treatment discontinuation” was added.

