2.3 Exploratory Objectives

2.3.1 To determine the 1-year progression-free survival (PFS) of HIV-infected women with locally-advanced invasive cervical cancer (LACC) Stage IB, II, III, and IVA who receive weekly cisplatin concomitant with radiotherapy and ART.

2.3.1.1 Determine PFS in all registered participants, regardless of completion (intent to treat-ITT)

2.3.1.2 Determine the PFS in the subset of participants who complete the prescribed chemotherapy/ radiotherapy

2.3.1.3 Compare PFS in these subjects with PFS of HIV-uninfected subjects as reported in the literature, stage for stage.

2.3.2 To describe the effects of treatment on participants' CD4 counts, HIV viral load and concurrent AIDS-defining conditions.

2.3.3 To describe cervical cancer recurrence patterns in HIV-infected participants with LACC defined as loco-regional and/or distant recurrences.

2.3.4 Determine 1-year overall survival and causes of death (i.e., cancer-related, HIV-related, or other).

2.3.5 To evaluate the effects of weekly cisplatin concomitant with radiotherapy on adherence to ART.

2.3.6 Collect serum and cervical and anal swab material for the following exploratory analyses:

2.3.6.1 To describe the distribution of HPV DNA types and HPV strain variants in cervical and anal swabs collected at baseline, prior to initiation of study treatment;

2.3.6.2 To assess the concordance between HPV DNA types and HPV strain variants detected in cervical and anal swabs collected at baseline, prior to initiation of study treatment;

2.3.6.3 To investigate the effect of study treatment on HPV persistence in cervical and anal swabs and its relationship to cervical cancer persistence or recurrence;

2.3.6.4 To describe the gene methylation profiles in cervical and anal swabs collected at baseline, prior to initiation of study treatment;

- 2.3.6.5 To investigate the relationship between baseline gene methylation profiles and cervical cancer persistence or recurrence;
- 2.3.6.6 To measure serum antibody titers to HPV 16 and HPV 18 at baseline and on study, and to determine whether baseline titers or changes during therapy correlate with cervical cancer persistence or recurrence.

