5.1.1 Within 28 days prior to initiating protocol therapy

- Medical history for eligibility
- Physical examination including: weight and height for BSA calculation, performance status (Refer to [Appendix II](#)), general physical exam, and pelvic exam if judged as necessary by the investigator.
- Tumor measurements and clinical staging
- CT scan with contrast of pelvis and abdomen
- Chest X-ray
- CD4+ T-cell count
- HIV viral load

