5.2 Evaluations during Chemo-Radiation Treatment

5.2.1 Weekly During Chemo-Radiation (Day 1, 8, 15, 22, 29, 36, (- 2 days))

The following laboratory results will be obtained on the same day or up to 2 days prior to cisplatin administration unless otherwise noted:

- CBC and differential
- Calculated creatinine clearance
- Electrolytes (sodium, potassium, chloride, magnesium)
- Review of interim medical history including concomitant medications and adverse events
- ART adherence assessment will be collected on Day 8, Day 15, Day 22, Day 29, and Day 36.

- Physical Examination on Day 22 prior to treatment.

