5.2.2 Assessments at the Time of Chemo-Radiation Therapy Completion

The following assessments must be completed within 7 days of chemo-radiation therapy completion unless otherwise specified. These assessments are required for all participants regardless of the reason for treatment discontinuation (e.g. treatment completion or early discontinuation).

- Review of interim medical history including concomitant medications and adverse events.
- ART adherence assessment.
- Physical examination.

The following assessments must be completed either on the final day of chemo-radiation therapy or within 4 weeks after the final dose of chemo-radiation therapy:

- Anal and cervical swabs to evaluate the exploratory study objectives (refer to [Appendix XI](#)).
- Serum to evaluate the exploratory study objectives (refer to [Appendix XI](#)).

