5.3 Evaluations after Completion of Therapy

Participants are to be followed at 3 intervals for 1 year after completing protocol treatment. CT imaging will be repeated at the 6-month time point after discontinuing treatment only for participants that have not clinically progressed; other imaging modalities can be employed off-study, as appropriate and at the discretion of the treating physician, at other time points. Participants that progress or relapse during the 12 month study follow-up period will be followed for survival only.

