5.3.1 Month 3 (+/- 4 weeks)

- Physical examination
- Review of interim medical history including concomitant medications and adverse events

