APPENDIX I: SCHEDULE OF EVENTS

The following observations and tests are to be performed and recorded on the appropriate form(s):

Tests and Observations	Prior to Entry	Weekly During Chemo-Radiation	Chemo-Radiation Therapy Completion or Premature Treatment Discontinuation ¹⁰	3, 6, 9, and 12 Month Follow-up	After Diagnosis of Recurrence	Premature Study Discontinuation ⁶
Medical History	X ¹					
Physical exam	X ¹	X ²	X ²	X ²		X
Tumor measurements and clinical staging	X ¹					
CT scan with contrast of pelvis and abdomen	X ¹			X ³	X	X
Chest X-ray †	X ¹				X	X ⁷
CD4+ T-cell count	X ¹			X ⁴	X	X ⁷
HIV viral load	X ¹			X ⁴	X	X ⁷
CBC + differential	X ⁵	X				X ⁷
Calculated creatinine clearance	X ⁵	X				X ⁷
SGOT, SGPT, alkaline phosphatase, bilirubin	X ⁵					X ⁷
Electrolytes (Na, K, Cl, Mg)	X ⁵	X				
Serum or urine pregnancy test *	X ⁵					X ⁸
Review of interim medical history		X	X	X ⁸	X	X
Slides for central pathology review	X ⁵					
ART Adherence		X	X	X		
Cytoscopy, IVP	X ^{5,+}					
Anal and cervical swabs for HPV-associated disease research	X ⁵		X ⁹			X
Serum for HPV-serology	X ⁵		X ⁹		X	X

X¹ Must be obtained within 28 days prior to initiating protocol therapy

X² At day 22 prior to treatment, at treatment discontinuation, and every 3 months for 1 year.

X³ CT with contrast of abdomen and pelvis to be done prior to study entry, 6 months +/- 4 weeks and 12 months +/- 4 weeks after concomitant chemoradiotherapy. Can perform CT without contrast only if recent creatinine ≥ 1.5 mg/dL (within 4 weeks of scan).

X⁴ Every 6 months while on protocol

X⁵ Must be obtained within 14 days prior to initiating protocol therapy. If ANC $\leq 1,500/\text{mm}^3$ ($1.5 \times 10^9/\text{L}$) or platelets $\leq 50,000/\text{mm}^3$ ($50 \times 10^9/\text{L}$), repeat twice per week until over these values or subject off trial.

X⁶ Evaluations should be performed whenever possible, preferably at the time of or up to 1 month after withdrawal from study.

- X⁷ Tests are required if not done within the last 3 months.
- X⁸ Every 3 months for 1 year.
- X⁹ Anal and cervical swabs and serum for HPV-associated disease research will be collected on the final day of chemo-radiation therapy or within 4 weeks following the final chemo-radiation therapy.
- X¹⁰ Assessments must be completed within 7 days of the completion of chemo-radiation therapy. This visit is required for all participants and refers to both to scheduled completion of treatment and premature treatment discontinuation

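### No pre-treatment ART adherence is collected, section 5.3 and Appendix I disagree on follow-up adherence, and the single proportion planned in section 11.1 does not estimate the effect named in exploratory objective 2.3.5

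*Combined protocol and SAP*

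**What the plan says.** Section 2.3.5 states the exploratory objective: "To evaluate the effects of weekly cisplatin concomitant with radiotherapy on adherence to ART". The synopsis repeats it. The trial has a single arm.

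Adherence appears in the schedule as follows.

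- **Before treatment.** Neither screening list in section 5.1 (the 28-day list, headed "Within 28 days prior to initiating protocol therapy", and the 14-day list) includes adherence. In the Appendix I row "ART Adherence", the prior-to-entry cell is blank.
- **During treatment.** Section 5.2.1 covers visits on Days 1, 8, 15, 22, 29 and 36, but for adherence it says: "ART adherence assessment will be collected on Day 8, Day 15, Day 22, Day 29, and Day 36".
- **At completion.** Section 5.2.2 lists one adherence assessment, under the instruction "The following assessments must be completed within 7 days of chemo-radiation therapy completion unless otherwise specified".
- **Follow-up.** Appendix I marks adherence in the column for months 3, 6, 9 and 12. Sections 5.3.1 to 5.3.4 list the procedures for those same visits. Each includes "Review of interim medical history including concomitant medications and adverse events", and none includes adherence.
- **After progression.** Section 5.3 says: "Participants that progress or relapse during the 12 month study follow-up period will be followed for survival only".

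Section 11.1 describes adherence assessments as weekly during cisplatin and at the end of therapy. It calls a woman inadherent if she reports missed doses at more than one assessment. The planned result is the proportion inadherent during protocol therapy, with an exact 95% confidence interval.

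**The concern.** The objective concerns an effect, but the planned analysis estimates a level. With no control arm, the trial's own data can speak to change only by comparing each woman's adherence on treatment with her adherence off it. The schedule has no measurement before treatment. The body text and Appendix I disagree on whether there is any in follow-up, and section 11.1 uses neither.

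Two things are at stake. The report could give an inadherence rate without being able to say whether it was already there before chemoradiation. Sites could also collect different data, because one working from section 5.3 would not ask about adherence in follow-up and one working from Appendix I would.

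**Working it through.** The documents give no sample size, power or effect size for adherence, so there is no figure to reproduce. The check sets the time points side by side and then examines the section 11.1 definition.

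**1. Time points**

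| Period | Body text (5.1 to 5.3) | Appendix I | Used in 11.1 |
|---|---|---|---|
| Before treatment | None | Blank | No |
| Weekly on treatment | Days 8, 15, 22, 29, 36 (5) | Marked | Yes |
| Completion | 1, within 7 days of completion | Marked | Yes |
| Months 3, 6, 9, 12 | None | Marked (4) | No |

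The analysis therefore draws on 5 + 1 = 6 assessments. The sixth may fall up to 7 days after treatment ends, so counting it as on-treatment is approximate. The Appendix I mark for the weekly visits gives no day list. Section 5.2.1 does, and it leaves out Day 1.

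**2. What the planned analysis returns**

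These are exact (Clopper-Pearson) 95% intervals. The counts are illustrative; 38 evaluable and 45 enrolled are the planned numbers.

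- 8/38 = 21%: 9.6% to 37.3%
- 11/38 = 29%: 15.4% to 45.9%
- 9/45 = 20%: 9.6% to 34.6%

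Each is a rate with its precision. None is a contrast with adherence off treatment, and a larger sample would narrow the interval without supplying one.

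**3. Whether the section 11.1 rule can carry a comparison**

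Let p be the chance of reporting a missed dose at any one assessment, assumed constant and independent across assessments, and let m be the number of assessments. Then

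P(inadherent) = 1 − (1 − p)^m − m·p·(1 − p)^(m − 1).

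For p = 0.10:

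- m = 6: 1 − 0.531441 − 0.354294 = 0.114
- m = 4: 1 − 0.6561 − 0.2916 = 0.052
- m = 1: 1 − 0.90 − 0.10 = 0

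| p (assumed) | 6 assessments to completion | 4 follow-up assessments | 1 baseline assessment |
|---|---|---|---|
| 0.05 | 0.033 | 0.014 | 0 |
| 0.10 | 0.114 | 0.052 | 0 |
| 0.20 | 0.345 | 0.181 | 0 |
| 0.30 | 0.580 | 0.348 | 0 |

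With no change in behaviour, the rule shows worse adherence on treatment than in follow-up, because there are more chances to report a miss. A single baseline assessment can never meet it. Any comparison between periods therefore needs an outcome defined at each assessment.

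**The case against.** The strongest reply is that Appendix I is an operative part of the protocol and schedules adherence at months 3, 6, 9 and 12. The summary of changes for version 3.0, cited only as context, shows that the entry was deliberate: "In the column 3, 6, 9 and 12 Month Follow-up, the following indications were added: Physical exam and ART adherence". An off-treatment, within-woman comparator is therefore scheduled, and a trend from Day 8 to completion could also be described. This stands. A reader might infer from the missing baseline and from section 11.1 that the trial has no comparator, that 2.3.5 cannot be answered, or that the effect is not estimable at any sample size. The documents do not support those readings.

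The follow-up comparator is nevertheless weak. Section 5.3 contradicts it, section 11.1 does not use it, women who progress leave it, and it is confounded with time.

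Further points on the other side:

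- A Day 1 measurement would not isolate the effect of cisplatin and radiotherapy. Section 4.2.3.1 lets women start ART on the day of enrolment, and section 3.1.5 admits non-suppressed women if an alternative regimen is available. A before/during/after comparison shows change, confounded with time and ART changes. This stands and limits what the fix can claim.
- The adherence form and its recall window are not in the documents, so whether the Day 8 questions reach back before Day 1 is unknown. This also stands.
- A proportion with an exact interval is a defensible descriptive summary in a 45-woman feasibility study, and viral load at screening and at months 6 and 12 gives indirect before/after information under 2.3.2. Both are fair. Neither makes the section 11.1 proportion an estimate of the effect named in 2.3.5.

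**Conclusion.** The point holds as a mismatch between an exploratory objective and its planned data and analysis. No adherence is collected before treatment, section 5.3 and Appendix I disagree at all four follow-up visits, and section 11.1 yields one on-treatment proportion. As planned, 2.3.5 would be described and not evaluated.

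The mismatch can be repaired. If sites follow Appendix I, up to four post-treatment assessments per woman are available. A Day 1 assessment would bring the off-treatment maximum to 1 + 4 = 5. That is a ceiling: women who progress contribute fewer, and women starting ART at enrolment have no baseline. The documents do not say how many women will already be on ART.

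The artefact calculation assumes independent assessments with a constant chance of a reported miss. The values of p are illustrative, and the direction is the same at all four. The finding is minor: it touches one exploratory objective, and neither the primary analysis nor any safety decision depends on it.

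**What to change.** 1. Add the same adherence assessment at the existing Day 1 visit, before the first cisplatin dose, for women already on ART. Mark it in Appendix I.
2. List adherence in sections 5.3.1 to 5.3.4 so that they match Appendix I.
3. In section 11.1, add a within-woman comparison of on-treatment adherence with pre- and post-treatment adherence. The outcome should be any missed dose reported at that assessment, analysed for example by GEE. The rule of more than one assessment can stay for the descriptive on-treatment proportion but should not be used to compare periods.
4. Report the result as a before/during/after change, confounded with time and with ART changes, and not as a causal effect. State that follow-up data come only from women who have not progressed.

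If no contrast is wanted, reword 2.3.5 and its synopsis counterpart as descriptive. Section 5.3 and Appendix I still need to agree.

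The cost is one extra assessment at a visit that already takes place, assumed short because the form is not in the documents, plus wording changes in sections 5.2.1, 5.3 and 11.1 and Appendix I. Women who start ART at enrolment will still have no baseline.

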5.2.2 Assessments at the Time of Chemo-Radiation Therapy Completion

The following assessments must be completed within 7 days of chemo-radiation therapy completion unless otherwise specified. These assessments are required for all participants regardless of the reason for treatment discontinuation (e.g. treatment completion or early discontinuation).

- Review of interim medical history including concomitant medications and adverse events.
- ART adherence assessment.
- Physical examination.

The following assessments must be completed either on the final day of chemo-radiation therapy or within 4 weeks after the final dose of chemo-radiation therapy:

- Anal and cervical swabs to evaluate the exploratory study objectives (refer to [Appendix XI](#)).
- Serum to evaluate the exploratory study objectives (refer to [Appendix XI](#)).

5.3 Evaluations after Completion of Therapy

Participants are to be followed at 3 intervals for 1 year after completing protocol treatment. CT imaging will be repeated at the 6-month time point after discontinuing treatment only for participants that have not clinically progressed; other imaging modalities can be employed off-study, as appropriate and at the discretion of the treating physician, at other time points. Participants that progress or relapse during the 12 month study follow-up period will be followed for survival only.

5.3.1 Month 3 (+/- 4 weeks)

- Physical examination
- Review of interim medical history including concomitant medications and adverse events

5.3.2 Month 6 (+/- 4 weeks)

- Physical examination
- CT scan with contrast of pelvis and abdomen
- CD4+ T-cell count
- HIV viral load
- Review of interim medical history including concomitant medications and adverse events

5.3.3 Month 9 (+/- 4 weeks)

- Physical examination
- Review of interim medical history including concomitant medications and adverse events

5.3.4 Month 12 (+/- 4 weeks)

- Physical examination
- CT scan with contrast of pelvis and abdomen
- CD4+ T-cell count
- HIV viral load
- Review of interim medical history including concomitant medications and adverse events

5.4 Evaluations after Diagnosis of Recurrence

For participants who experience a recurrence of disease, the following evaluations should be performed, preferably at the time of or up to 2 weeks after diagnosis:

- CT scan with contrast of pelvis and abdomen
- Chest X-ray
- CD4+ T-cell count
- HIV viral load
- Review of interim medical history including concomitant medications and adverse events
- Serum to evaluate the exploratory study objectives (refer to [Appendix XI](#))

Participants will only be followed for survival following the diagnosis of disease progression or recurrence. Treatment for progressive/recurrent disease will be at the discretion of the site investigator and will not be coordinated or paid for as part of the study.

5.5 Premature Study Discontinuation Evaluations

For participants who withdraw from the study prematurely (discontinuation prior to 12 month follow-up for any reason), the following evaluations should be performed whenever possible, preferably at the time of or up to 1 month after withdrawal from the study:

- Physical examination
- If more than 3 months after last CT scan, CT scan with contrast of pelvis and abdomen
- Review of interim medical history including concomitant medications and adverse events
- If not done within 3 months of withdraw date, the following diagnostic and laboratory tests should be done:
 - Chest X-ray
 - CD4+ T-cell count
 - HIV viral load
 - CBC and differential
 - Calculated creatinine clearance
 - SGOT, SGPT, alkaline phosphatase, bilirubin
 - Electrolytes (sodium, potassium, chloride, magnesium)

6.0 TREATMENT MODIFICATIONS

6.1 Radiation Therapy

It is in the participant's best interest to receive the radiation therapy on time. Every effort should be made to encourage the participant to comply with the radiation treatment prescribed where possible since time to completion of therapy is correlated with survival. The goal is to complete radiation therapy in 56 days.

6.1.1 Expected Toxicity

All toxicities will be graded according to the Common Toxicity Criteria (CTCAE v4.0).

6.1.1.1 Blood/Bone Marrow (Hematologic)

Hematologic toxicity is seen infrequently unless pelvic radiation is accompanied by chemotherapy. A CBC should be obtained weekly, and if the ANC falls below $1500/\text{mm}^3$ ($1.5 \times 10^9/\text{L}$) or the platelet count drops below $100,000/\text{mm}^3$ ($100.0 \times 10^9/\text{L}$), counts should be obtained twice weekly. Treatment may proceed if $\text{ANC} > 1000/\text{mm}^3$ ($1.0 \times 10^9/\text{L}$), and platelet count $> 50,000/\text{mm}^3$ ($50.0 \times 10^9/\text{L}$).

Every effort should be made to maintain hemoglobin $\geq 10\text{g/dL}$ (6.2 mmol/L). It is up to the individual investigator's discretion as to how best to achieve this.

6.1.1.2 Gastrointestinal

Nausea and vomiting is rather unusual after pelvic radiation. If nausea occurs, the subsequent use of prophylactic antiemetics is strongly encouraged. Antiemetic regimens are at the discretion of the investigator. Anti-emetics may be given when symptoms occur if not given prophylactically prior to treatment. Intractable nausea or vomiting is rarely seen with pelvic radiation alone and is usually the result of another process, i.e., bowel obstruction. Increased bowel activity with diarrhea usually can be controlled with low fiber, low fat, bland diets and antidiarrheal medications. Should GI toxicity become severe, hospitalization may be required at which time the treatment may be interrupted temporarily until the participant's condition improves. This interruption should be limited to ≤ 1 week if possible (Refer to [Section 6.1.2](#)).

